#### 1.3 RATIONALE FOR PERFORMING THE TRIAL

The combination of BI 1358894 and oral contraceptives containing EE and DRSP may be widely used in a clinical setting.

the aim of this study is to investigate any possible drug-drug interaction to assure the safe and effective use of COCs with BI 1358894.

There is evidence that EE containing oral contraceptives have only a very small effect on CYP3A4 activity as determined by midazolam metabolism [P05-12887, R03-1002, R03-1128]. The pharmacokinetics of telapravir, a hepatitic C virus protease inhibitor and substrate of CYP3A4, were not changed by coadministration of ethinylestradiol/norethindrone

of CYP3A4, were not changed by coadministration of ethinylestradiol /norethindrone [R12-0031].

c41232811-04 Trial Protocol Page 20 of 84

Proprietary confidential information © 2023 Boehringer Ingelheim International GmbH or one or more of its affiliated companies

#### 1.4 BENEFIT - RISK ASSESSMENT

## 1.4.1 Benefits

Participation in this clinical trial is without any (therapeutic) benefit for healthy subjects. Their participation, however, is of major importance for the development of BI 1358894.

#### 1.4.2 Risks

Subjects are exposed to risks of trial procedures and risks related to the exposure to the trial medication.

The trial staff will supervise the correct taking of the COC. Thus, a failure rate of less than 1% can be assumed. Pregnancy testing will also be implemented at different times of the study.

An overview of trial-related risks is given in Table 1.4.2: 1

Table 1.4.2: 1 Overview of trial-related risks for this trial

Possible or known risks of clinical relevance	Summary of data, rationale for the risk	Mitigation strategy
Inve	stigational Medicinal Product: BI	1358894

**Trial Protocol** 

Page 21 of 84

Table 1.4.2: 1 Overview of trial-related risks for this trial (cont.)

Possible or known risks of clinical relevance	Summary of data, rationale for the risk	Mitigation strategy
Inve	estigational Medicinal Product: BI	1358894
In	vestigational Medicinal Product: Y	
Increased risk of venous and arterial thromboembolism	The incidence of venous thromboembolic events is 2 per 10000 women in one year, if no hormonal contraceptives are used. The incidence is increased to 9 - 12 per 10000 women after intake of COC containing drospirenone [R23-0484].  The risk of venous thromboembolism increases in the presence of pre-existing risk factors such as obesity, immobilization, family history of thromboembolism, hypercoagulability states and increased age.  Epidemiologic studies showed that the use of COC increases the risk of arterial thromboembolism (myocardial infarct) and cerebrovascular events (transient ischaemic attack, stroke). The risk increases when there are pre-existing conditions such as older age, smoking, arterial hypertension, obesity, family history, migraine, prothesis valves, atrial fibrillation, dyslipidaemia, lupus) [R23-0484]	- Close monitoring of adverse events, safety lab, ECG and vital signs - Subjects with additional risk factors will not be allowed in participation in the trial - Subjects with a recent history of malignancy within 5 years (except appropriately treated basal cell carcinoma of the skin) will be excluded from participation - In case of occurrence of a serious side effect, trial treatment to be discontinued, and diagnostics and treatment have to be initiated according to local standard of care - In addition to the general inclusion examination, the suitability of subjects for taking this oral contraceptive will be assessed by a gynaecologist prior to trial entry

c41232811-04 Trial Protocol Page 22 of 84

Table 1.4.2: 1 Overview of trial-related risks for this trial (cont.)

Possible or known risks of clinical relevance	Summary of data, rationale for the risk	Mitigation strategy		
Investigational Medicinal Product: Yasmin®				
Increased risk of tumors	Some epidemiologic data suggest the presence of increased incidence of cervix carcinoma. The data is not clear in this respect (SmPC of Yasmin).  A metanalysis of 54 epidemiologic studies showed a light increase risk (RR = 1.24) in breast cancer in women who take COC. The risk goes back to baseline within 10 years of stopping the COC [R23-0484].  In rare cases it was observed the presence of malignant liver neoplasms in women taking COCs [R23-0484].	- Close monitoring of signs and symptoms that suggest the presence of malignancy - Subjects with a recent history of malignancy within 5 years (except appropriately treated basal cell carcinoma of the skin) will be excluded from participation. Subjects with any history of breast cancer will be excluded from the trial.		
Risk of hyperkalaemia	Due to the aldosterone agonism of drospirenone possible increase in the kalium concentration can occur. This is particularly important in patients with mild to moderate renal insufficiency [R23-0484].	- Only subjects with normal kidney function will be allowed in the trial		
The most frequent side effects of Yasmin® are:  - Headache  - Migraine  - Nausea  - Spotting and intermenstrual bleeding  - Irregularities of menstrual cycle  - Breast tenderness  - Depressive mood  - Vulvovaginal candidiasis	Menstrual changes associated with the use of oral contraceptives include reduction of menstrual flow and missed menstruation.  Intermenstrual bleeding may occur but normally ceases spontaneously.  Based on SmPC of Yasmin®  [R23-0484]	- Symptomatic treatment of headache and breast tenderness if required - Treatment of vulvovaginal candidiasis if required - Treatment with Yasmin® should be continued even if irregular bleeding occurs as it normally ceases spontaneously - If irregular bleeding is persistent, appropriate diagnostic measures to exclude an organic cause are indicated - Women with history of migraine or major depressive disorder will be excluded		

c41232811-04 Trial Protocol Page 23 of 84

Table 1.4.2: 1 Overview of trial-related risks for this trial (cont.)

Possible or known risks of clinical relevance	Summary of data, rationale for the risk	Mitigation strategy	
Investigational Medicinal Product: Yasmin®			
The following undesirable effects have been observed:  - Changes in libido  - Hypertension  - Hypotension  - Vomiting  - Diarrhea  - Acne, Eczema, pruritus, alopecia  - Breast hypertrophy  - Vaginal infection  - Fluid retention  - Weight changes	Based on SmPC of Yasmin® [R23-0484]	- Increased awareness of symptoms - Symptomatic treatment if required - If required, further diagnostics and treatment have to be initiated according to local standard of care	
Drug-drug interaction between Yasmin® and other drugs	CYP3A4 inhibitors or inducers may impact the exposure of oral contraceptives. Whereas an increase of exposure may increase the number and intensity of side effects, a decrease would result in reduced efficacy.	Subjects will not be allowed to use other drugs which may interfere with Yasmin® in accordance to the SmPC within 30 days before start of run-in period (including moderate and strong CYP3A4 inhibitors, CYP3A4 inducers, grapefruit juice, St. John's wort (Hypericum perforatum), etc.)	

c41232811-04 Trial Protocol Page 24 of 84

Proprietary confidential information © 2023 Boehringer Ingelheim International GmbH or one or more of its affiliated companies

Table 1.4.2: 1 Overview of trial-related risks for this trial (cont.)

Possible or known risks of clinical relevance	Summary of data, rationale for the risk	Mitigation strategy		
Trial procedures				
Bruising and, in rare cases, phlebitis, or nerve injury, potentially resulting in paresthesia, reduced sensibility, and/or pain	General risk by venipuncture for blood sampling, acceptable in the framework of trial participation.	Medical expertise of the trial site		
General risk of psychoactive drugs				
Impaired thinking, judgment, and/or motor skills	Because psychoactive drugs may impair thinking, judgment, and/or motor skills, patients should be cautioned about operating machinery, including automobiles, until they are reasonably certain that the study medication does not adversely affect their ability to engage in such activities. It is recommended that patients should exercise caution when driving or operating machinery	Participants should be cautioned about operating machinery, including automobiles, until they are reasonably certain that the study medication does not adversely affect their ability to engage in such activities.		

The total volume of blood withdrawn per subject during the entire trial will not exceed the volume of a normal blood donation (500 mL). No health-related risk to healthy subjects is expected from withdrawal of this volume of blood.

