# CLINICAL TRIAL PROTOCOL SYNOPSIS

Company name	Boehringer Ingelheim
Original protocol date	06 Mar 2023
Revision date	19 Oct 2023
BI trial number	1402-0019
Title of trial	An open-label, fixed-sequence cross-over, two-period, phase I trial to evaluate the effect of multiple doses of BI 1358894 on pharmacokinetics of a combination of ethinylestradiol and drospirenone in healthy female subjects
Investigator	
Trial site	
Clinical phase	I
Trial rationale	o further inform on prescription possibilities of BI 1358894 together with oral contraceptives, this investigation of potential drug-drug interaction aims to assure safe and effective use of oral contraceptives if combined with BI 1358894
Trial objective	To investigate the effect of multiple oral doses of BI 1358894 on pharmacokinetics of ethinylestradiol (EE) and drospirenone (DRSP) (Yasmin®)
Trial endpoints	Primary endpoints:  • AUC \tau,ss , and C \text{max,ss} of EE and DRSP in plasma  Secondary endpoint:  • C \text{min,ss} of EE and DRSP in plasma
Trial design	Open-label, two-period, fixed-sequence with a run-in period
Number of subjects total entered on each treatment Diagnosis	32 32 Not applicable
Main inclusion criteria	Healthy female subjects, premenopausal, age of 18 to 35 years (inclusive), body mass index (BMI) of 18.5 to 29.9 kg/m² (inclusive)

c41232811-04 Trial Protocol

Page 3 of 84

Test product 1	BI 1358894, film-coated tablets, dose strength and
dose	
mode of administration	Oral with 240 mL of water after a continental breakfast
Test product 2	Yasmin®, film-coated tablets
dose	30 microgram ethinylestradiol + 3 milligram drospirenone q.d.
mode of admin.	Oral with 240 mL of water after a continental breakfast
Duration of treatment	
 
Run-in period: 
 
1 tablet of Yasmin® q.d. for 21-49 days
 
 
 
Reference treatment (Period 1): 
 
1 tablet of Yasmin® q.d on study days 1 – 21
 
 
 
Test treatment (Period 2): 
 
1 tablet of Yasmin® q.d. +1
 
on study days 1 – 21
 
 
 

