# FLOW CHART

Period	Visit	Day	Planned time (relative to first drug administration) [h:min]	Approximate clock time of actual day [h:min]	Event and comment	Safety laboratory	PK plasma, BI 1358894	PK plasma, COC	Exploratory PD serum 	12-lead ECG	Vital signs (BP, PR)	Suicidality Assessment 	Questioning for AEs and concomitant therapy 
SCR	1	-91 to -			Screening (SCR) 	$A^6$				X	X	X	
Run	2	-56 to -			Self-administration of COC	x 							Х
-in 		-7 to -1			Follow up call (COC free interval)								х
	3	1	0:00	08:00	Dosing COC 	$\mathbf{B}^{8}$		x 	x 				X
		2	24:00	08:00	Dosing COC 								X
		3	48:00	08:00	Dosing COC 								X
		4	72:00	08:00	Dosing COC 								X
		5	96:00	08:00	Dosing COC 								X
		6	120:00	08:00	Dosing COC 								X
		7	144:00	08:00	Dosing COC 								X
		8	168:00	08:00	Dosing COC 								X
		9	192:00	08:00	Dosing COC 								X
		10	216:00	08:00	Dosing COC 	x 							X
		11	240:00	08:00	Dosing COC 								X
		12	264:00	08:00	Dosing COC 								Х
		13	288:00	08:00	Dosing COC 								X
		14	312:00	08:00	Dosing COC 								X
-		15	336:00	08:00	Dosing COC 								X
Period 1		16	360:00	08:00	Dosing COC 								X
Per		17	384:00	08:00	Dosing COC 								X
		18	408:00	08:00									X
		19	432:00	08:00	Dosing COC 								X
		20	456:00	08:00	Dosing COC 								X
			466:00	18:00	Admission to trial site	x 					X		X
		21	479:30	07:30	Start of continental breakfast								X
			480:00	08:00	Dosing COC 			x 	x 				X
			480:30	08:30				X					X
			481:00	09:00				X					X
			481:30	09:30				X					X
			482:00	10:00	240 mL fluid intake			X					X
			482:30	10:30				X					X
			483:00	11:00		-		X					X
			483:30	11:30	040 7 0 11 1 7 12			X					X
			484:00	12:00	240 mL fluid intake, Lunch 			X					X

c41232811-04 Trial Protocol

Page 5 of 84

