- 7. The intake of Yasmin® starts depending on the subjects' actual menstruation cycle and at least -28 days before Day 1 of first treatment period. In the run-in period, the subjects will take one tablet of COC daily until Day -8. On Day 7 to Day -1 no COC tablets will be given in order to induce withdrawal bleeding. Self-administration in the morning with no requirement of fasting. Self-administration to be documented in the diary. A negative urine pregnancy test should be performed at the site 1 to 7 days before start of the run-in. Details are outlined in Section 4.1.4
- 8. Urine pregnancy test. Additional urine drug screening on day 20 of each period.
- 9. Blood collection takes place within 10 minutes before dosing.
- 10. Suicidality assessment using the Columbia-Suicidal Severity Rating Scale (C-SSRS): 'Screening/Baseline' version at Visit 1, and 'since last visit' version at other visits.
- 11. Measurement of exploratory pharmacodynamic parameters: estradiol, luteinizing hormone (LH), follicle stimulating hormone (FSH), and progesterone. The samples will be taken in duplicate.
- 12. Dosing at the trial site after a continental breakfast (for details see Section 4.1.4).

c41232811-04 Trial Protocol

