## 1.2.2.3 Safety

Combined oral contraceptives (COC) including Yasmin® should not be used in the following conditions. Should any of the conditions appear for the first time during COC use, the product should be stopped immediately.

- Presence or risk of venous thromboembolism (VTE)
- Presence or risk of arterial thromboembolism (ATE)
- Presence or history of severe hepatic disease or liver tumors
- Current or history of breast cancer
- Hypersensitivity to the active substances or to any of the excipients

The frequency of diagnosis of breast cancer is very slightly increased among COC users. As breast cancer is rare in women under 40 years of age the excess number is small in relation to the overall risk of breast cancer. Causation with COC use is unknown.

The most common adverse events with Yasmin® are nausea, headache, migraine, depressed mood, menstrual cycle alteration, breast tenderness, vaginal discharge and candidiasis vulvovaginal altered mood, breast pain, and breast tenderness.

Less common adverse events are changes in the libido, hypertension, hypotension, vomiting, diarrhoea, acne, eczema, pruritus, alopecia, breast hypertrophy, vaginal infections, fluid retention and weight changes.

Rare adverse events are hypersensitive reactions, asthma, hearing loss, venous and arterial thromboembolism, erythema nodosum, erythema multiforme and discharge of the mammary glands.

Drospirenone, as many other progestogens, has been linked to increased risk of venous thromboembolism [R23-0501] A statement from FDA concluded that the increase in the risk of thromboembolism resulting from the use of drospirenone remains unclear; in its statement, the FDA mentioned that increased risk of venous thromboembolism with oral contraceptives such as drospirenone exists but remains lower than the risk of this condition during pregnancy and during the postpartum period [R23-0680].

c41232811-04 Trial Protocol

Page 19 of 84

Proprietary confidential information © 2023 Boehringer Ingelheim International GmbH or one or more of its affiliated companies

For a complete listing of adverse reactions including frequency of occurrence please refer to the current version of the summary of product characteristics (SmPC) [R23-0484].

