## 3. DESCRIPTION OF DESIGN AND TRIAL POPULATION

#### 3.1 OVERALL TRIAL DESIGN

The trial will be performed as a non-randomised, open-label, two-period, fixed sequence trial with run-in period in healthy female subjects in order to compare the test treatment (T) to the reference treatment (R).

Reference (R): one tablet of Yasmin® q.d. after a continental breakfast on Days 1-21 in Period 1.

Test (T): one tablet of Yasmin® q.d.  $\pm$  one tablet of BI 1358894 25 mg q.d.  $\pm$  two tablets of BI 1358894 50 mg q.d. after a continental breakfast on Days 1-21 in Period 2.

[figure not shown]
The Reference Treatment will always be followed by the Test Treatment in a fixed sequence. There will be no wash-out period between the treatments.

All subjects will undergo a run-in period that starts between Day -56 and Day -28. In this period, the subjects will take one tablet of Yasmin® daily until Day -8.

In the last 7 days of each treatment period (i.e., Day 22 to Day 28) and the run-in period (i.e. Day -7 to Day -1) no treatment will be given in order to induce bleeding.

For details, refer to Section 4.1.

An overview of all relevant trial activities is provided in the Flow Chart. For visit schedule and details of trial procedures at selected visits, refer to Section 6.1 and 6.2, respectively.

Abbreviation: R=Reference Treatment (Yasmin®); T=Test Treatment (Yasmin® and BI 1358894)

Figure 3.1: 1 Trial design

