#### 4.1.4 Drug assignment and administration of doses for each subject

This trial is a non-randomised trial with two periods. All subjects will receive the two treatments in a fixed order. The treatments to be evaluated are summarised in Table 4.1.4: 1 below.

Table 4.1.4: 1 Dosage and treatment schedule

Treatment	Substance	Formulation	Unit strength	Dosage	Total daily dose
R (Reference)	Yasmin®	Tablet	30 ug EE /3 mg DRSP	1 tablet q.d. (Period 1, Days 1-21)	30 ug EE /3 mg DRSP
T (Test)	Yasmin®	Tablet	30 ug EE /3 mg DRSP	1 tablet q.d. (Period 2, Days 1-21)	30 ug EE /3 mg DRSP
	BI 1358894				

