#### 5.7 APPROPRIATENESS OF MEASUREMENTS

All measurements performed during this trial are standard measurements and will be performed in order to monitor subjects' safety and to determine pharmacokinetic parameters in an appropriate way. The scheduled measurements will allow monitoring of changes in vital signs, standard laboratory values, and ECG parameters that might occur as a result of administration of trial medication. The safety assessments are standard, are accepted for evaluation of safety and tolerability of an orally administered drug, and are widely used in clinical trials. The pharmacokinetic parameters and measurements outlined in Section 5.3 are generally used assessments of drug exposure. The pharmacodynamic biomarkers measurements outlined in Section 5.4 are of exploratory nature only.

Proprietary confidential information © 2023 Boehringer Ingelheim International GmbH or one or more of its affiliated companies

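### The risk table and Section 5.7 rely on monitoring of vital signs, but the legible Flow Chart marks no blood pressure or pulse between screening and the evening of Period 1 Day 20, 47 to 75 days after the first COC tablet

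*Protocol*

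**What the plan says.** In Table 1.4.2: 1, the Yasmin row on venous and arterial thromboembolism opens its mitigation column with "Close monitoring of adverse events, safety lab, ECG and vital signs". The same row counts arterial hypertension among the conditions that raise arterial risk. Section 1.2.2.3 lists blood pressure changes among the effects of Yasmin: "Less common adverse events are changes in the libido, hypertension, hypotension, vomiting". Section 5.7 makes the general claim: "The scheduled measurements will allow monitoring of changes in vital signs, standard laboratory values, and ECG parameters that might occur as a result of" giving trial medication.

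The Flow Chart sets the schedule. After screening, the first mark in the vital-signs column is at 18:00 on Period 1 Day 20, in the row "Admission to trial site". The other marks are Period 1 Day 22, Period 2 Day 20 (18:00), Period 2 Day 22 and end of study. The run-in rows carry only the urine pregnancy test and questioning for adverse events. Day 1 of each period carries safety laboratory set B but no vital signs. Sections 6.2.1 and 6.2.2 add no time point. The eligibility re-check before run-in (Section 4.1.3) names no measurement.

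**The concern.** The protocol offers vital-signs monitoring as a safeguard against a serious risk in healthy volunteers, who have no therapeutic benefit from taking part (Section 1.4.1). If the schedule takes no reading during most of the planned COC exposure, that safeguard is weaker than an ethics committee or investigator would take it to be.

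There is also a data consequence. Vital signs are a declared safety assessment (Section 2.2.2.3), and Section 7.2.5 provides for assigning measurements to the run-in, yet none is scheduled there.

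**Working it through.** No plan figure states the share of tablets taken before the first reading, so it has to be counted. Full adherence to the planned dosing is assumed.

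**Inputs**
- Run-in start: "All subjects will undergo a run-in period that starts between Day -56 and Day -28" (Section 3.1).
- Last run-in tablet: "the subjects will take one tablet of COC daily until Day -8" (Flow Chart, footnote 7).
- Periods 1 and 2: 21 tablets each (Table 4.1.4: 1).
- First reading after COC starts: Period 1 Day 20 at 18:00, after that morning's dose (Flow Chart). There is no Day 0.

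**Step 1: reproduce the plan's own figure.** Run-in tablets = last day − first day + 1.
- Start Day −56: −8 + 56 + 1 = 49.
- Start Day −28: −8 + 28 + 1 = 21.

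Both match the synopsis: "1 tablet of Yasmin® q.d. for 21-49 days".

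**Step 2: share of tablets before the first reading.** Share = (run-in + 20) / (run-in + 21 + 21).
- Shortest run-in: (21 + 20) / (21 + 42) = 41/63 = 65.1%.
- Longest run-in: (49 + 20) / (49 + 42) = 69/91 = 75.8%.
- Periods 1 and 2 only: 20/42 = 47.6%.

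**Step 3: elapsed time from first tablet to first reading.**
- Shortest run-in: 28 + 19 = 47 days.
- Longest run-in: 56 + 19 = 75 days.
- From the earliest screening day (Day −91): 91 + 19 = 110 days. With the longest run-in, 91 − 56 = 35 of these precede any COC.

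**Step 4: ECG.** The first ECG after COC starts is on Period 1 Day 22, after 21 Period 1 tablets.
- Shortest run-in: 42/63 = 66.7%.
- Longest run-in: 70/91 = 76.9%.

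**Step 5: BI 1358894.** The first reading in Period 2 is at 18:00 on Day 20, after 20 of 21 doses.

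**The case against.** **Close monitoring has no stated frequency.** The mitigation bullet covers four kinds of assessment, and two are denser: adverse events are asked about on essentially every dosing day, and safety laboratory set B is taken on Day 1 of each period. Section 5.7 says only that changes can be monitored, and a pre-COC value plus two readings at the end of each period does allow some comparison. This stands. It rules out calling the schedule a breach of a defined rule, and it confines the point to vital signs and ECG.

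**Hypertension has its own row.** A reader might infer that the protocol promises vital-signs monitoring for hypertension as a Yasmin effect. It does not. That row of Table 1.4.2: 1 offers awareness of symptoms, symptomatic treatment and further diagnostics. The promise sits in the thromboembolism row, where hypertension is a pre-existing risk condition. Another bullet there excludes subjects with additional risk factors, and exclusion criterion 2 screens on blood pressure.

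**The larger percentages depend on the denominator.** The 65 to 76% includes tablets of a marketed product taken at home. Within Periods 1 and 2 the figure is 48%. This is correct, and both belong in the record.

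**Missing Day 1 values are not a defect in themselves.** Safety baseline is the last value before first trial medication (Section 7.2.5). Day 22 of each period gives a matched comparison, and Period 1 Day 22 is seven days before the first BI 1358894 dose. A Period 1 Day 1 pre-dose value would follow the tablet-free week. This also stands.

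**The source text is damaged.** Section 5.2.2 breaks off mid-sentence, and a few other Flow Chart cells are lost. Timing text in 5.2.2 cannot be excluded. The vital-signs marks that remain are nevertheless consistent across both periods.

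**The trial stopped in the run-in.** No subject started Period 1 (SAP Section 4), so no added reading in Periods 1 or 2 would have been reached. This limits the practical value of a schedule change for this trial, but not the mismatch in the text.

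**Conclusion.** The mismatch holds at reduced strength. No legible text schedules blood pressure or pulse in the run-in or on Days 1 to 19 of either period, while two statements in the protocol lean on such monitoring. The gap is 47 to 75 days from the first tablet and 65 to 76% of all planned COC tablets (48% within Periods 1 and 2). In Period 2 it is 20 of 21 BI 1358894 doses. These figures rest on the planned dosing, on the Flow Chart marks as they can be read, and on Section 5.2.2 containing no further time points.

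A reader might go further and infer that a rise in blood pressure would pass without symptoms and so go unnoticed. The documents say nothing on whether such a rise causes symptoms. Section 5.2.6.2.1 also has medical staff assess subjects regularly and whenever the investigator sees need. Nor can a breached mitigation for BI 1358894 be inferred, because its risk rows are not visible.

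For the trial as it ended, 28 subjects took COC in the run-in (SAP Section 6.1) with no scheduled vital signs in that phase. The change-from-baseline listing in SAP Section 7.8.3 therefore depends on end-of-study or unscheduled readings.

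**What to change.** Reconcile the Flow Chart with the thromboembolism row of Table 1.4.2: 1 and with Section 5.7, and check the full text of Section 5.2.2 while doing so. There are two ways:

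- **Extend the schedule.** Mark blood pressure and pulse at on-site visits that already take place, for example those where safety laboratory set B or a urine test is already done. The sponsor chooses the time points. The cost is a few minutes per visit, a few more values to list and one Flow Chart amendment, with no extra visit or blood draw. Readings added in Periods 1 and 2 would not cover the home run-in: one taken before dosing on Day 10 would still follow 30/63 (21 + 9 tablets; 48%) to 58/91 (49 + 9 tablets; 64%) of planned tablets. The text should then say what is measured in the run-in and what is not.
- **Narrow the wording.** Limit the mitigation and Section 5.7 to the readings the schedule contains, for both vital signs and ECG. This costs only a text change.

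Since the trial has stopped, the practical use is in the clinical trial report, which should not describe vital signs as closely monitored in the run-in without saying when they were taken, and in any reuse of this design.
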